#### **9.4.4.5. Nausea and Vomiting**

Nausea and vomiting events are considered AEs of interest and will be recorded as AEs in the eCRF. For event assessment of severity, duration, and investigator's opinion of relatedness to IP and protocol procedure will be captured.

#### **9.4.4.6. Thyroid Malignancies and C-Cell Hyperplasia**

Individuals with personal or family history of MTC and/or MEN-2 will be excluded from the study. The assessment of thyroid safety during the trial will include reporting of any case of thyroid malignancy including MTC and papillary carcinoma and measurements of calcitonin. This data will be captured in specific eCRFs. The purpose of calcitonin measurements is to assess the potential of tirzepatide to affect thyroid C-cell function, which may indicate development of C-cell hyperplasia and neoplasms. Tirzepatide should be discontinued (after first confirming the value) if post randomization calcitonin value is  $\geq 35$  ng/L (pg/mL) and has increased at least 50% over baseline. A consultation with a thyroid specialist (if not available, an endocrinologist) should be obtained.

If the increased calcitonin value ( $\geq 35$  pg/mL and increases by  $\geq 50\%$  compared to baseline) is observed in a patient who has administered a medication that is known to increase serum calcitonin, this medication should be stopped and calcitonin levels should be measured after an appropriate wash out period. If the confirmed calcitonin value is  $< 35$  pg/mL, tirzepatide should be restarted when it is safe to do so.

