### Treatment Arms and Planned Duration for an Individual patient:

This study consists of 2 cohorts. Approximately 12 Chinese patients with T2DM will be randomized within a cohort to receive tirzepatide or placebo. For Cohort 1, 16 weekly SC doses of tirzepatide or placebo will be administered in a ratio of 10 tirzepatide:2 placebo. For Cohort 2, 24 weekly SC doses of tirzepatide or placebo will be administered in a ratio of 10 tirzepatide:2 placebo.

Patients in Cohort 1 will receive either tirzepatide with titration regimen starting from 2.5 mg for Days 1, 8, 15, and 22 (Weeks 0 to 3), 5 mg for Days 29, 36, 43, and 50 (Weeks 4 to 7), 7.5 mg for Days 57, 64, 71, and 78 (Weeks 8 to 11), and 10 mg for Days 85, 92, 99, and 106 (Weeks 12 to 15), or corresponding volume-matched placebo.

Patients in Cohort 2 will receive either tirzepatide with titration regimen starting from 2.5 mg for Days 1, 8, 15, and 22 (Weeks 0 to 3), 5 mg for Days 29, 36, 43, and 50 (Weeks 4 to 7), 7.5 mg for Days 57, 64, 71, and 78 (Weeks 8 to

11), 10 mg for Days 85, 92, 99, and 106 (Weeks 12 to 15), 12.5 mg for Days 113, 120, 127, and 134 (Weeks 16 to 19), and 15 mg for Days 141, 148, 155, and 162 (Weeks 20 to 23), or corresponding volume-matched placebo.

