a A patient who discontinues from Cohort 1 between Day 1 and Day 113, inclusive, will complete ED1 procedures as soon as possible. The patient will be asked to complete ED2 procedures after a washout period of at least 28 days from the last IP administration. The patient who discontinues from Cohort 1 after the completion of Day 113 will complete ED2 procedures after a washout period of at least 28 days from the last IP administration. A patient who discontinues from Cohort 2 between Day 1 and Day 169, inclusive, will complete ED1 procedures as soon as possible. The patient will be asked to complete ED2 procedures after a washout period of at least 28 days from the last IP administration. The patient who discontinues from Cohort 2 after the completion of Day 169 will complete ED2 procedures after a washout period of at least 28 days from the last IP administration.

b Patients will be required to fast overnight for at least 8 hours before taking the first SC dose of tirzepatide (or placebo) and before each blood sample draw on fasting visit.

c Weight will be measured in a consistent way per Section 9.1, always predose.

d Full physical examination / medical assessment at screening. Symptom-directed physical examination/medical assessment at all other time points, and as deemed necessary by the investigator.

e Patients who have completed chest x-ray within the past 12 months and whose x-ray and/or report are available for review are exempt from the chest x-ray examination. The required chest x-ray is a single posterior anterior (PA) x-ray. If evidence of an abnormality, a lateral chest x-ray will be performed.

f These tests will be performed at the local laboratory.

g Additional urine drug screen or breath ethanol tests may be performed at the investigator's discretion.

h Females only. Blood pregnancy test will be done on screening; urine test at other times as indicated, or when performed at the investigator's discretion.

i Patients will conduct the 7-point SMPG every 3 days since Day -13 during lead-in period and will record readings in patient diary.

j A maximum of 3 samples may be collected at additional time points during the study if warranted and agreed upon by both the investigator and sponsor.

k Patients may be required to remain at the CRU longer than the planned discharge day at the investigator's discretion to assure patients' safety or to provide additional safety monitoring.

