### 8.1. Discontinuation from Study Treatment

Discontinuation of the IP for abnormal liver tests should be considered by the investigator when a patient meets 1 of the following conditions after consultation with the Lilly-designated medical monitor:

- ALT or AST  $>8X$  ULN
- ALT or AST  $>5X$  ULN sustained for more than 2 weeks or
- ALT or AST  $>3X$  ULN and TBL  $>2X$  ULN or international normalized ratio  $>1.5$  or
- ALT or AST  $>3X$  ULN with the appearance of fatigue, nausea, vomiting, right upper-quadrant pain or tenderness, fever, rash, and/or eosinophilia ( $>5\%$ )
- alkaline phosphatase (ALP)  $>3X$  ULN
- ALP  $>2.5X$  ULN and TBL  $>2X$  ULN
- ALP  $>2.5X$  ULN with the appearance of fatigue, nausea, vomiting, right quadrant pain or tenderness, fever, rash, and/or eosinophilia ( $>5\%$ ).

In addition, a patient will be discontinued from using the IP in case of abnormal pancreatic tests when he or she meets the following condition:

- lipase and/or amylase are confirmed to be  $\geq 3 \times$  ULN. Please refer to the algorithm for the monitoring of pancreatic events in [Appendix 5](#).

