### Protocol I8F-MC-GPHT Sampling Summary

Purpose	Blood Volume per Sample (mL)	Number of Blood Samples		Total Volume (mL)	
		Cohort 1	Cohort 2	Cohort 1	Cohort 2
Screening serology and serum pregnancy tests a	9 b	1	1	9	9
Clinical safety laboratory tests a	10 b	12	13	120	130
Lipid panel	2.5	6	8	15	20
Pancreatic enzyme	3	9	10	27	30
Calcitonin	2.5	3	3	7.5	7.5
Tirzepatide pharmacokinetics	3	24	26	72	78
Potential additional tirzepatide pharmacokinetic samples	3	3	3	9	9
Fasting blood glucose	4.5	6	8	27	36
HbA1c	2	6	8	12	16
Immunogenicity	10	6	6	60	60
Pharmacogenetics	10	1	1	10	10
Total				369 c	406 c

Abbreviation: HbA1c = hemoglobin A1c.

a Additional samples may be drawn if needed for safety purposes.

b Because screening and safety (chemistry and hematology) tests are performed at local laboratories at each site, this volume is an estimate and will vary depending on the local laboratory's testing requirements.

c The maximum blood volume will increase if follow-up visits for antidrug antibody testing are needed.

---

**Appendix 6. Protocol Amendment I8F-MC-GPHT(b)  
Summary - A Multiple Dose Titration Study in Chinese  
Patients with Type 2 Diabetes Mellitus to Investigate the  
Safety, Tolerability, Pharmacokinetics, Pharmacodynamics,  
and Efficacy of Tirzepatide**

---

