### **9.6.6 Thyroid Malignancies and C-Cell Hyperplasia**

The assessment of thyroid safety during the trial will include reporting of any case of thyroid malignancy including medullary thyroid carcinoma and papillary carcinoma and measurements of calcitonin.

Calcitonin data will be summarized by treatment and timepoint together with changes from baseline, where baseline is defined as the Day 1 predose assessment.

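### The calcitonin stop and restart rules have no scheduled value to act on while doses remain: a continuing patient's only post-baseline sample comes after the last dose

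*Protocol*

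**What the plan says.** **The rule.** Protocol Section 9.4.4.6: "Tirzepatide should be discontinued (after first confirming the value) if post randomization calcitonin value is" 35 ng/L or more and at least 50% above baseline. A thyroid specialist, or failing that an endocrinologist, is then consulted. If the patient was taking another medicine known to raise calcitonin, that medicine is stopped and calcitonin is measured again after washout. If the confirmed value is then below 35 pg/mL, "tirzepatide should be restarted when it is safe to do so".

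**The baseline.** SAP Section 9.6.6: "Calcitonin data will be summarized by treatment and timepoint together with changes from baseline, where baseline is defined as the Day 1 predose assessment".

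**The doses.** In Protocol Section 1, the last step in Cohort 1 is "10 mg for Days 85, 92, 99, and 106 (Weeks 12 to 15" and the last step in Cohort 2 is "15 mg for Days 141, 148, 155, and 162 (Weeks 20 to 23".

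**The samples.** Protocol Section 2 schedules calcitonin at screening, Day 1 predose, the end-of-treatment visit (Day 113 in Cohort 1, Day 169 in Cohort 2) and ED1. Neither the follow-up visits nor ED2 include it. ED1 is conditional on stopping. Footnote a reads "A patient who discontinues from Cohort 1 between Day 1 and Day 113, inclusive, will complete ED1 procedures as soon as possible", and Cohort 2 has the same provision through Day 169. Appendix 5 plans 3 calcitonin samples of 2.5 mL per patient in each cohort.

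**The concern.** Stopping and restarting act on doses not yet given, so the rule needs a calcitonin result while dosing is under way. The schedule provides none. A patient whose calcitonin crossed the threshold during titration would receive every remaining dose unless someone happened to order an unscheduled test. Section 9.4.4.6 names no trigger for such a test. Calcitonin is also not part of the routine chemistry panel in Appendix 2, where it is listed separately and assayed at a sponsor-designated laboratory.

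The protocol's other enzyme-type stopping rule is supported by its schedule. Section 8.1 stops treatment when "lipase and/or amylase are confirmed to be" at least 3 times the upper limit of normal, and the "Pancreatic enzyme" row of Appendix 5 plans 9 samples in Cohort 1 and 10 in Cohort 2, including predose samples on Days 29, 57 and 85.

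**Working it through.** **1. Reproduce the plan's own sample count.** For a patient who continues to the end, the Schedule of Activities gives screening (1) + Day 1 predose (1) + Day 113 or Day 169 (1) = 3 samples, and 3 × 2.5 mL = 7.5 mL. Appendix 5 states 3 samples and 7.5 mL in each cohort. The budget therefore has no room for a further on-treatment sample.

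**2. Dose days.** Dosing is weekly from Day 1, so dose *k* falls on Day 1 + 7(*k* − 1).
- Cohort 1: dose 16 is on Day 1 + 7 × 15 = Day 106. First to last dose: 106 − 1 = 105 days.
- Cohort 2: dose 24 is on Day 1 + 7 × 23 = Day 162. First to last dose: 162 − 1 = 161 days.

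**3. Scheduled calcitonin after Day 1 predose and up to the last dose.** There is none in either cohort. Day 1 predose is the baseline, so it cannot show a rise over itself.

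**4. Position of the first scheduled post-baseline value.**
- Cohort 1: 113 − 106 = 7 days after the last dose; doses remaining, 0 of 16.
- Cohort 2: 169 − 162 = 7 days after the last dose; doses remaining, 0 of 24.

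One caveat on the inputs: in the extracted text the Cohort 1 calcitonin row appears displaced by one column. Day 113 is inferred from the Appendix 5 count and from the Cohort 2 row, which aligns exactly with Day 169 and ED1. Read literally, the Cohort 1 mark would fall on Day 109. That is still 109 − 106 = 3 days after the last dose, so the conclusion is the same.

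**5. What an on-treatment sample would allow.** For a predose sample on Day *s* and a confirmed result *t* days later, the doses that can still be withheld number (last dose day − (*s* + *t*))/7 + 1. The documents give no turnaround, so *t* = 7, 14 and 21 days are assumptions. Example, Cohort 1, *s* = 57, *t* = 7: (106 − 64)/7 + 1 = 7.

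| Sample day | Cohort 1, *t* = 7 / 14 / 21 | Cohort 2, *t* = 7 / 14 / 21 |
|---|---|---|
| Day 57 | 7 / 6 / 5 of 16 | 15 / 14 / 13 of 24 |
| Day 85 | 3 / 2 / 1 of 16 | 11 / 10 / 9 of 24 |
| Day 113 | none left | 7 / 6 / 5 of 24 |
| Day 141 | none left | 3 / 2 / 1 of 24 |

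**The case against.** The rule is not tied to scheduled samples. It covers any post-randomization value, so it can act on an unscheduled test, and a standing rule of that kind does not contradict the schedule. The stated purpose of measuring calcitonin, to look for an effect on C-cell function, is served by comparing Day 1 with a value taken 7 days after the last dose. About 20 patients receive tirzepatide, after exclusion [16] (personal or family history of medullary thyroid carcinoma, or MEN-2) and exclusion [17] (calcitonin of 35 ng/L or more), and the documents give no rate at which the threshold is crossed. Nor does frequent pancreatic sampling show that every marker with a stopping rule needs the same frequency; Section 9.4.4.2 itself says that serial enzymes predict poorly in patients without symptoms.

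Much of this is fair, and it limits the claim. The end-of-treatment value still supports confirmation, specialist consultation and the SAP summary. The expected number of patients affected cannot be stated. The pancreatic comparison shows only that on-treatment sampling is feasible. But entry exclusions deal with risk at baseline, whereas the rule prescribes an action on dosing afterwards, and an unscheduled test that nothing prompts is not a working safeguard.

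The proposed days can also be questioned. Eight doses (Days 1 to 50) precede a Day 57 sample, and a Day 29 sample would come with 12 doses (Cohort 1) and 20 (Cohort 2) still to give. In Cohort 2 the Day 113 predose sample precedes the first 12.5 mg dose, so it says nothing about 12.5 or 15 mg. Section 7.6 discontinues a patient who misses 4 or more doses without saying whether doses withheld under Section 9.4.4.6 count, which leaves the restart clause uncertain. Finally, stopping patients could reduce the roughly 16 completers sought, with no replacement planned. These points bear on how to refine the remedy. The follow-up costs come from a rule the protocol already contains.

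**Conclusion.** The concern holds. In a continuing patient, no scheduled calcitonin value can trigger the stop or restart in Section 9.4.4.6 while any dose remains, in either cohort. This follows from the schedule, the dose days and the Appendix 5 count, and does not depend on how the displaced Cohort 1 row is read. The gap concerns scheduled monitoring: the rule could still act on an unscheduled value. The only assumption is the turnaround of 1 to 3 weeks, which affects how many doses an added sample could save but not the finding itself. No claim is made about how often the threshold would be crossed. The plan should be changed because it states a patient-safety rule that its schedule does not support and the remedy is cheap.

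**What to change.** Add a predose calcitonin sample on Days 57 and 85 in both cohorts and on Day 113 in Cohort 2, all visits where blood is already drawn. Keep Day 113 (Cohort 1) and Day 169 (Cohort 2) as the end-of-treatment value. Update the Schedule of Activities, and raise the Appendix 5 counts from 3 to 5 in Cohort 1 and from 3 to 6 in Cohort 2.

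Cost, at 2.5 mL per sample (the Appendix 5 rows sum to 368.5 and 405.5 mL, printed as 369 and 406):
- Cohort 1: 368.5 + 2 × 2.5 = 373.5 mL (+1.4%), 2 more assays per patient.
- Cohort 2: 405.5 + 3 × 2.5 = 413.0 mL (+1.8%), 3 more assays per patient.

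No visit or venipuncture is added. As an optional refinement, a Day 141 predose sample in Cohort 2 would give a value after the 12.5 mg step, for a further 2.5 mL (415.5 mL, +2.5% over the present total).

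Two wording changes would help at no sampling cost: state in Section 9.4.4.6 that the rule also applies to unscheduled values and what follows a high end-of-treatment result, and state in Section 7.6 whether doses withheld under this rule count as missed.

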### **9.5. Pharmacokinetics**

At the visits and times specified in the Schedule of Activities (Section 2), venous blood samples of approximately 3 mL each will be collected to determine the plasma concentrations of tirzepatide. A maximum of 3 samples may be collected at additional time points during the study if warranted and agreed upon between both the investigator and sponsor. Instructions for the collection and handling of blood samples will be provided by the sponsor. The actual date and time (24-hour time period) of each sampling will be recorded.

Drug concentration information that may unblind the study will not be reported to study sites or blinded personnel until the study has been unblinded.

### ***9.5.1. Bioanalysis***

A laboratory approved by the sponsor will analyze samples. A facility designated by the sponsor will store samples.

Concentrations of tirzepatide will be assayed using a validated liquid chromatography mass spectrometry method. Analyses of samples collected from patient who received placebo are not planned.

Bioanalytical samples collected to measure IP concentrations will be retained for a maximum of 1 year following last patient visit for the study.

## **9.6. Pharmacodynamics**

Assessment of tirzepatide pharmacology may include lipid profile (total cholesterol, high-density lipoprotein and low-density lipoprotein cholesterol, triglycerides), meal intake and appetite, and immunogenicity assessments. Additional exploratory PD analysis may be analyzed as deemed appropriate.

Blood samples will be obtained for the measurement of PD. The scheduled times for the collection of these samples are as listed in the Schedule of Activities (Section 2). The timing of PD samples is intended to assess pharmacologic effects of tirzepatide. The sampling times may be modified at the discretion of the sponsor, but the total number of the samples or total blood volume will not increase.

The sample(s) will be stored for up to a maximum of 1 year after the last patient visit for the study at a facility selected by the sponsor. The chemistry panel will be destroyed in 60 days and 7-point samples will not be stored.

### ***9.6.1. Lipids***

Lipid profile (total cholesterol, high-density lipoprotein, very low-density lipoprotein, and triglycerides), as indicated in the Schedule of Activities (Section 2), will be assayed using validated analytical methods. Instructions for the collection and handling of blood samples for these analyses will be provided by the sponsor.

### ***9.6.2. Meal Intake and Appetite***

To explore the effects of tirzepatide on meal intake and appetite sensation, patients will be provided standardized lunch and dinner meals with an approximate total energy and macronutrient contents of 700 kCal and 20% protein, 25% fat, and 55% carbohydrate according to the Schedule of Activities (Section 2). The meal intake will be recorded in the source

document. The subjective rating of appetite sensations is measured using a 100-mm visual analogue scale (VAS) for parameters of hunger, fullness, satiety, and prospective food consumption before and 4 to 5 hours after the standardized lunch and dinner meals. The standardized lunch and dinner meals will be provided at least 4 hours after the previous meal. The VAS is a validated tool to assess appetite sensation parameters (Flint et al. 2000). The VAS is presented as a 10-cm (100-mm) line, anchored by verbal descriptors, usually “extremely” and “not at all.” Patients are required to rate their subjective sensations on four 100-mm scales combined with the questions: “How hungry do you feel right now?”, “How satisfied do you feel right now?”, “How full do you feel right now?”, and “How much food do you think you could eat right now?” A staff member will use a caliper to measure the distance from 0 to the mark that the patient placed on the VAS and record the measurement in the source document. Overall appetite score is calculated as the average of the 4 individual scores—satiety + fullness + (100-prospective food consumption) + (100-hunger) / 4 (van Can et al. 2014). The higher overall appetite score indicates less appetite, and the lower score indicates more appetite.

### **9.6.3. Immunogenicity Assessments**

At the visits and times specified in the Schedule of Activities (Section 2), venous blood samples will be collected to determine antidrug antibody (ADA) production against the tirzepatide. To interpret the results of immunogenicity, a venous blood sample will be collected at the same time point to determine the plasma concentrations of tirzepatide. All samples for immunogenicity should be taken predose when applicable and possible. All patients will have an ADA sample measured at early discontinuation or at the follow-up visit (Day 141 for Cohort 1 and Day 197 for Cohort 2) approximately 5 weeks after the last dose of tirzepatide. Follow-up visit will assess immunogenicity at washout of tirzepatide (5 half-lives at the end of treatment).

In the event of a drug hypersensitivity reaction, see Section 9.4.4.3 for instructions of collection and handling of blood samples.

Immunogenicity will be assessed using a validated assay designed to detect and titer ADA in the presence of tirzepatide at a laboratory approved by the sponsor. Samples with detected ADA will be tested for cross-reactive binding to native GIP and GLP-1. Antibodies may be further evaluated for their ability to neutralize the activity of tirzepatide. In vivo laboratory indicators for glycemic control (fasting blood glucose and HbA1c), effect on weight loss, and PK will be utilized to detect potential neutralizing effect of ADA against tirzepatide.

Treatment-emergent (TE) ADAs are defined in Section 10.3.5.

Antidrug antibody samples will be stored as per local regulation/EC requirements. Samples will be immediately destroyed once tirzepatide is launched or there is no further request on testing the samples from China authority.

## 9.7. Genetics

A blood sample will be collected for pharmacogenetic analysis as specified in the Schedule of Activities (Section 2), where local regulations allow.

Samples will not be used to conduct unspecified disease or population genetic research either now or in the future. Samples will be used to investigate variable exposure or response to tirzepatide and to investigate genetic variants thought to play a role in T2DM. Assessment of variable response may include evaluation of AEs or differences in efficacy.

All samples will be coded with the patient number. These samples and any data generated can be linked back to the patient only by the investigative site personnel.

Samples will be retained for a maximum of 15 years after the last patient visit, or for a shorter period if local regulations and/or ERBs impose shorter time limits, for the study at a facility selected by Lilly. This retention period enables use of new technologies, response to regulatory questions, and investigation of variable response that may not be observed until later in the development of tirzepatide or after tirzepatide is commercially available.

Molecular technologies are expected to improve during the 15-year storage period and therefore cannot be specifically named. However, existing approaches include whole genome or exome sequencing, genome-wide association studies, multiplex assays, and candidate gene studies. Regardless of technology utilized, data generated will be used only for the specific research scope described in this section.

